regimen prescribed should be recorded on the Concomitant medication CRF under the immunosuppressive category and any CNI trough levels should be recorded on the appropriate local lab trough CRF.

For subjects who have discontinued randomized study regimen, visits need only be completed at Months 6, 9, 12, 18 and 24. For all subjects completing the study to Month 12 or discontinuing from the study prior to Month 12, the M12 Period completion form should be completed, regardless of on or off-treatment status. Similarly post-Month 12, for all subjects completing the study to Month 24 or discontinuing from the study prior to Month 24, the M24 Period completion form should be completed, regardless of on or off-treatment status.

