9.4.3 Handling of missing values/censoring/discontinuations

Since the subjects who have prematurely discontinued study regimen are followed on standard of care, renal function data (e.g. creatinine) and kidney allograft biopsy data will be collected post discontinuation of study regimen for these visits, it is expected that few subjects would be missing efficacy and/or renal function evaluation for the 12 month analysis.

To define the primary variable – composite endpoint of tBPAR or eGFR (MDRD4) < 50 mL/min/1.73m², the following imputation method will be applied for subjects with missing 12month eGFR value. As allograft biopsy data will be collected on an as needed basis due to the nature of kidney transplant studies, no particular rule for missing biopsy will be applied.

- Under the assumption of missing not at random (MNAR), subjects who lost their grafts will be assigned a value of zero for their 12-month eGFR;
- Otherwise, under the assumption of missing at random (MAR), subjects who had missing values including those who died with a functioning graft will have a 12-month eGFR imputed using multiple imputation method based on the longitudinal eGFR (MDRD4) data at all available time points and covariates of randomization strata (donor type and CNI), HLA mismatches ($\leq 3 \text{ vs} > 3$) and induction.

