#### Testing of CNI effects:

Based on FAS without imputation, treatment by CNI interaction for the composite endpoint of tBPAR or eGFR (MDRD4) < 50 mL/min/1.73m^2 will be assessed using a logistic regression model including covariates/factors for treatment, CNI, region, interaction of treatment and CNI, interaction of treatment and region, donor type, HLA mismatch ( $\leq 3$  vs  $> 3$ ), induction therapy, recipient gender, recipient age, donor age, DGF, and eGFR (MDRD4) at Month 1. In the model, recipient and donor age will be treated as continuous variables. If the interaction is not significant at the level of 0.10, i.e. the effects of treatment are similar for each CNI, then the primary analysis will be based on the pooled CNIs, i.e. everolimus plus reduced CNI (EVR+rCNI) vs. MPA plus standard CNI (MPA+sCNI). If this test shows significantly different event rates for tacrolimus vs. cyclosporine, then testing will be performed for the 2 CNIs separately, with the tacrolimus subgroup being considered primary [REDACTED]

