#### The alternative hypothesis:

$H_{A1}$ :  $R_{\text{EVR+rCNI}} - R_{\text{MPA+sCNI}} < 0.10$  (non-inferiority margin): The difference in proportion of patients experiencing tBPAR or eGFR (MDRD4)  $< 50 \text{ mL/min/1.73m}^2$  at 12 months between the everolimus plus reduced CNI ( $R_{\text{EVR+rCNI}}$ ) and the MPA plus standard CNI arm ( $R_{\text{MPA+sCNI}}$ ) is less than 10%.

The proportion of patients meeting the primary endpoint of tBPAR or eGFR (MDRD4)  $< 50 \text{ mL/min/1.73m}^2$  at Month 12 will be compared using a confidence interval approach.

Multiple imputation will be used as the primary method for handling missing data (see [Section 2.5.3](#) and [Section 4.2.1.1](#) for detail). The analysis first creates multiple (100) imputations of missing eGFR (MDRD4) values under a missing at random (MAR) assumption, resulting in multiple (100) imputed datasets. The imputation model assumes a multivariate normal model for the eGFR (MDRD4) measurements. This model will be estimated separately within each treatment stratum. Together with the tBPAR data, the binary composite endpoint of tBPAR or eGFR (MDRD4)  $< 50 \text{ mL/min/1.73m}^2$  at Month 12 post-transplantation will be derived.

To the resulting 100 imputed datasets, the proportion of patients meeting the primary endpoint of tBPAR or eGFR (MDRD4)  $< 50 \text{ mL/min/1.73m}^2$  at Month 12 will be estimated, yielding 100 sets of parameter estimates and associated covariance matrices. The analysis results are then combined according to Rubin's rules to derive overall estimates and confidence intervals that adequately reflect missing data uncertainty as well as associated p-values (see [Section 4.7.1](#) for sample analysis codes). The everolimus plus reduced CNI arm will be claimed to have a

non-inferior incidence of tBPAR or eGFR (MDRD4)  $< 50$  mL/min/1.73m^2 compared to the MPA plus standard CNI arm if the upper limit of the 95% CI is below 10%.

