## 4.2 Missing Data Handling

### 4.2.1 Missing GFR Data Imputation

#### 4.2.1.1 Main Imputation

The following is the main imputation method for handling missing eGFR data at Month 12. A similar imputation rule can be applied for missing eGFR at Month 24. These imputations will be applied to the primary analyses for the composite endpoint of tBPAR or eGFR < 50 mL/min/1.73m^2, as well as for eGFR alone. For the component of eGFR < 50 mL/min/1.73m^2, a value for missing eGFR as a continuous variable will be imputed first, then it will be dichotomized in order to derive this endpoint.

- Under the assumption of missing not at random (MNAR), patients who lost their grafts will be assigned a value of zero for their missing eGFR at the visits on and after graft loss;
- Multiple imputation: Otherwise, under the assumption of missing at random (MAR), patients who had missing values including those who died with a functioning graft will have a 12-month eGFR imputed using multiple imputation method based on the covariates/factors CNI, region, donor type, HLA mismatch ( $\leq 3$  vs  $> 3$ ), induction therapy, recipient gender, recipient age, donor age, and DGF, and all eGFR (MDRD4) data collected at the visit windows during the analysis period of interest. In the multiple imputation, recipient age, donor age and eGFR (MDRD4) data will be treated as continuous variables. To help preserve the relationship between outcome and covariates within each treatment, a separate model will be run for each treatment. This will also help ensure that the imputation model does not make stronger assumptions on data relations than the analysis model.

To ensure that results can be replicated, the data should be sorted by patient number before running the model (the data should be in horizontal format with one row per patient). If there are multiple renal function assessments within a visit window, guidelines given in [Section 2.1](#) will be followed, i.e., the closest value to the planned visit (midpoint of visit window for post-baseline visits) will be taken (if tie, the last will be used) for imputation. In addition, the seed used in the multiple imputation will be 2433.

See dummy SAS codes below.

```
proc mi data=DATAIN out=DATAOUT nimpute=100 seed=2433;
  by treatment;
  class CNI region donor HLA induction gender_r DGF;
```

```
fcs reg (/details);  
var CNI region donor HLA induction gender_r age_r age_d DGF GFR_vis1  
GFR_VIS2 ... GFR_VISm;  
run;

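### The test that decides whether to pool the two CNIs uses a different version of the endpoint from the primary analysis and adjusts for two post-randomisation variables, so it can miss a treatment-by-CNI difference that the primary endpoint counts

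*SAP*

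**What the plan says.** **Pooling test (SAP 2.5.2, Testing of CNI effects).** The rule opens "Based on FAS without imputation, treatment by CNI interaction for the composite endpoint of tBPAR or eGFR (MDRD4" and goes on to a logistic model. Besides treatment, CNI, region, two interactions, donor type and HLA mismatch, the covariates are "induction therapy, recipient gender, recipient age, donor age, DGF, and eGFR (MDRD4) at Month 1". If the interaction is not significant at 0.10, the primary analysis is pooled. Otherwise, "then testing will be performed for the 2 CNIs separately, with the tacrolimus subgroup being considered primary". The text after that is blacked out, and nothing here rests on it. The same result decides whether eGFR is summarised by CNI (SAP 2.7.3.2).

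**Primary analysis (SAP 2.5.2.1, 4.2.1.1, 4.7.1).** The estimate is made on imputed data: "To the resulting 100 imputed datasets, the proportion of patients meeting the primary endpoint of tBPAR or eGFR (MDRD4" below 50 is estimated in each dataset and combined by Rubin's rules. The sample code is an unadjusted risk difference. Under the main imputation, "patients who lost their grafts will be assigned a value of zero for their missing eGFR at the visits on and after graft loss". Other missing values, including those after death with a functioning graft, are multiply imputed. The imputation model has CNI as a factor and "a separate model will be run for each treatment". Protocol 9.4.3 has the same graft-loss rule: "subjects who lost their grafts will be assigned a value of zero for their 12-month eGFR".

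**Protocol model for the test.** Protocol 9.4.2 refers to the risk-factor model of 9.4.4, which uses the subgroup variables listed there plus treatment-by-CNI and treatment-by-region. Neither Month 1 eGFR nor DGF is in that list, and the section does not confine the test to unimputed data.

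**Timing.** Month 1 is the Week 4 visit (Protocol 9.5.2), Days 22-44 in SAP Table 4-1. DGF is assessed within 21 days of transplant (SAP 2.3.2). In Protocol Table 6-1 the Week 4 central laboratory draw is only for patients still on regimen, and its footnotes add: "For subjects who have discontinued randomized study regimen, visits need only be completed at Months 6, 9, 12, 18 and 24".

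**The concern.** A test that chooses the population for the primary analysis should address the quantity that analysis estimates. This one departs from it in two ways.

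1. **Endpoint and patients.** The graft-loss zero rule is part of the imputation method. Without it, a graft loss with no tBPAR and no Month 12 value is a certain event in the primary analysis but not in the test. Deaths with a functioning graft, and patients without a Week 4 eGFR, can also fall out.
2. **Covariates.** Month 1 eGFR and DGF arise after randomisation, when the arms already follow different CNI targets (Protocol Table 5-1). If everolimus affects early renal function differently under the two CNIs, conditioning on early function removes that part of the interaction. The primary endpoint counts it.

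At stake is the choice between one pooled comparison (1020 per arm) and separate comparisons with tacrolimus as primary (816 per arm at the planned 80/20 split).

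**Working it through.** **Step 1. The plan's own figures.** Non-inferiority power = Φ(0.10/√(2·0.5·0.5/n) − 1.96), with 50% in both arms and a 10-point margin.
- n = 1020: 0.10/0.02214 = 4.52; Φ(2.56) = 99.5% (Protocol Table 9-1: >99).
- n = 816: 0.10/0.02475 = 4.04; Φ(2.08) = 98.1% (Table 9-1: 98).

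These reproduce and are not in dispute. The documents give no power or patient number for the interaction test.

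**Step 2. How each analysis treats a patient.**

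| Patient | Primary analysis | Pooling test as written |
|---|---|---|
| Graft loss, no tBPAR, no Month 12 eGFR | Event (eGFR = 0) | No outcome, or a non-event if so coded |
| Death with functioning graft, no tBPAR, no Month 12 eGFR | Imputed | No outcome, or a non-event if so coded |
| Month 12 status known, no Week 4 eGFR | Counted | Dropped for a missing covariate |

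The SAP does not say whether an unknown outcome is dropped or counted as a non-event. Neither reading matches the primary endpoint.

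**Step 3. Scenario.** EVR is 10 points worse under cyclosporine and equal under tacrolimus.
- Pooled difference: 0.8·0 + 0.2·10 = 2 points.
- SE = √(0.50·0.50/1020 + 0.52·0.48/1020) = 0.0221.
- Pooled non-inferiority power: Φ(0.08/0.0221 − 1.96) = 95.1%.

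**Step 4. An aligned test, closed form.** With cells of 816 and 204 per arm, SE of the interaction = √(2·0.25·(1/816 + 1/204)) = 0.0554. Power at two-sided 0.10 = Φ(0.10/0.0554 − 1.645) = 56.5%. If 5, 10, 15 or 20% of patients are lost, it is 54.7, 52.8, 50.9 or 48.9%. Loss of numbers alone therefore costs little.

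**Step 5. Simulation of the scenario** (2500 trials per setting).
- From the protocol: 816 + 204 per arm; eGFR SD 20 (Section 1.1 gives 19.5 and 20).
- Assumed: mean Month 12 eGFR 53; tBPAR 10%, independent of eGFR; Month 1 to Month 12 correlation 0.5 or 0.7; graft loss, other missing Month 12 and missing Week 4 of 2/3/3% or 4/8/8%, at random.
- Control rate: 1 − 0.9·(1 − Φ(−0.15)) = 49.6%, close to the planned 50%. A fall of 5.6 mL/min gives 1 − 0.9·(1 − Φ(0.13)) = 59.7%, or +10 points.
- Aligned test: treatment, CNI and their interaction on all 2040, graft loss as event, true values where the SAP would impute (slightly optimistic). As-written test: adds Month 1 eGFR, complete cases only. The other SAP covariates, including DGF, were left out of both.

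| Share of effect present at Month 1 | Aligned test detects | As-written test detects | Change from Month 1 adjustment alone |
|---|---|---|---|
| None | 55-56% | 53-63% | +4 to +10 points |
| Half | 55-56% | 35-40% | −14 to −18 points |
| All | 53-58% | 15-23% | −30 to −41 points |

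Repeat runs agreed closely; with all of the effect at Month 1 they reached up to 27%. Dropping patients alone cost 1-7 points. With no interaction, the as-written test rejected in 10-11% and the aligned test in 9-11%.

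**Step 6. Graft loss on its own.** In 1000 further runs (SD 16, correlation 0.64, no eGFR effect), graft loss was 12% in EVR with cyclosporine and 3% elsewhere. The aligned test rejected in 21% of runs and the as-written test in 11%, near its nominal level. Coding unknown outcomes as non-events gave 17%, but then the extra graft losses count in favour of everolimus.

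**The case against.** **Other checks exist.** A reader might infer that this test is the only safeguard against pooling over a CNI difference. It is the only formal one. CNI is a pre-specified subgroup (SAP 2.2.1), analysed by methods like those of the primary analysis (SAP 2.5.4.3), so a difference would still be shown descriptively. The futility reviewers may also assess poolability (SAP 2.12.1). This stands.

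**No false claim.** A reader might infer that non-inferiority would be wrongly claimed. In the scenario the true pooled difference is 2 points, inside the margin, so the claim is true for the pooled population. After a split, tacrolimus (true difference 0) would succeed in about 98% of trials. Even the aligned test would pool and claim non-inferiority in 41-45% of trials. This stands, as does the intact type I error.

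**The loss depends on an undocumented input.** With no effect at Month 1, adjustment helps. By target midpoints in Protocol Table 5-1, the EVR/MPA exposure ratio is 5.5/10 = 0.55 (tacrolimus) and 125/250 = 0.50 (cyclosporine) up to Month 2, then 3/6.5 = 0.46 and 37.5/150 = 0.25 after Month 6. The contrast between CNIs thus widens late, which argues against the all-early extreme. It does not exclude a partial early effect: the arms differ from Day 1, and Protocol 3.3 expects lower CNI exposure to improve renal function.

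**Missing patients may be few.** The SAP expects few missing Month 12 evaluations, realigns unscheduled assessments (4.1), and the protocol asks for local creatinine when no central value exists for off-regimen patients (Table 6-1, footnotes). Some Week 4 values may be recovered. This stands.

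**DGF follows the protocol's rule.** Protocol 9.4.4 builds the model from the subgroup variables, and the SAP added DGF to that list. That explains its presence, but DGF remains post-randomisation. Its separate effect was not calculated.

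**Conclusion.** The mismatch is in the text and no other section removes it. The pooling test leaves out events that are certain in the primary analysis, and it conditions on two variables that treatment may already have affected. It should be fixed.

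The adjustment matters more than the missing patients. In the illustrative scenario, detection is about 55% with an aligned test. As written it is about 53-63%, 35-40% or 15-25% with none, half or all of the effect present at Month 1; missing patients alone account for about 1-7 points. These figures rest on assumed graft-loss and missingness rates, an assumed Month 1 to Month 12 correlation and an assumed early share, none of which the documents give. They show direction and possible size, not a forecast.

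The documents do not support reading this as an inflated error rate or a false non-inferiority claim. What can be lost is the decision to analyse the CNIs separately when they differ.

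**What to change.** Rewrite the paragraph on testing CNI effects in SAP 2.5.2 so that the interaction test:
- is fitted in each of the 100 imputed datasets of the primary analysis, with eGFR set to zero after graft loss;
- is combined by Rubin's rules and judged at 0.10 as now;
- adjusts only for variables known at randomisation, omitting Month 1 eGFR and DGF.

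Keep the present model as a sensitivity analysis, and state there how graft loss and unknown outcomes are coded. The imputation model already supports the change, because it is fitted separately by treatment with CNI as a factor.

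The cost is one paragraph and a few lines of code on existing datasets, with no new data. The downside is slightly lower power for the interaction test if no effect is present at Month 1 (4-10 points of adjustment gain forgone, partly offset by keeping all patients).

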### 2.2.1 Subgroup of Interest

The following demographic/baseline characteristics are defined at the study level as subgroups for specified analyses:

- Recipient characteristics:
  - Age group: <60 vs ≥60 yr
  - Gender
  - Race: Caucasian, Black, Asian and All other races
  - Region: US, EU, Asia, Australia, Latin America, and Middle East

- DGF (delayed graft function)
- BMI <30 and  $\geq 30$
- Donor/transplant characteristics:
  - Age group: <60 vs  $\geq 60$  yr
  - Gender
  - Cold ischemia time: < 20 vs  $\geq 20$  hr
  - End stage disease leading to transplant (Glomerular disease, Diabetes mellitus and All other diseases)
  - Donor type (living donor, standard criteria and expanded criteria deceased donor): donor type will be derived based on Kidney Donor Background Information eCRF, and not the randomization stratification from IRT.
  - HLA mismatches:  $\leq 3$  vs  $> 3$
- CNI (tacrolimus vs. cyclosporine)
- Induction (basiliximab vs. rATG):
  - Basiliximab: preferred term: BASILIXIMAB; drug code/ID: 10892631
  - rATG: preferred term: ANTITHYMOCYTE IMMUNOGLOBULIN, or ANTITHYMOCYTE IMMUNOGLOBULIN (RABBIT); drug code/ID: 10878131 or 10878151

As early use of rATG can be for delayed graft function, type of induction will be identified as the first intake of rATG or basiliximab by Day 1 post-transplant.

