#### Testing strategy to control type I error:

Event rates will be compared between groups using the following hierarchical testing strategy:

- a. Non-inferiority of EVR+rCNI vs. MPA+sCNI will be evaluated based on the primary endpoint of tBPAR or eGFR (MDRD4)  $< 50 \text{ mL/min/1.73m}^2$  at Month 12 using a 10% non-inferiority margin (see [Section 2.5.2.1](#)).
- b. Non-inferiority of EVR+rCNI vs. MPA+sCNI will be evaluated with a 10% non-inferiority margin for the key secondary endpoint of tBPAR, graft loss or death at Month 12 (see [Section 2.6.2](#)).
- c. Superiority of EVR+rCNI to MPA+sCNI will be evaluated based on the primary endpoint of tBPAR or eGFR (MDRD4)  $< 50 \text{ mL/min/1.73m}^2$  at Month 12 (see [Section 2.5.2.2](#)).

The above hierarchical fixed hypothesis testing procedure will not inflate overall Type I error rate. Therefore, each hypothesis will be tested at the one-sided 0.025 significance level and no multiplicity adjustment is needed. For these statistical tests, one-sided p-values will be presented in the analysis outputs.

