### 3 Determination of Sample Size

The sample size for this study was chosen with the goals to (1) have high power to evaluate non-inferiority in both the overall population *and* the TAC alone population and (2) have adequate power to evaluate superiority in the both the overall population *and* the TAC alone population.

With a sample size of n=1020 randomized per arm (EVR, MPA), the study has at least 95% power to demonstrate non-inferiority ( $\alpha=0.025$ , one-sided) in the overall and TAC alone populations at Month 12. There are at least 73% and 63% power ( $\alpha=0.025$ , one-sided) to demonstrate superiority of 7% or more in the overall and TAC alone populations, respectively.

The calculations are based on the following assumptions:

- 80% of patients are randomized to tacrolimus, 20% of patients are randomized to cyclosporine

- 20% and 30% patients are excluded from the PP population at Months 12 and 24 respectively
- For non-inferiority, the event rate in each arm is 50%, based on study results from RAD001A2309 and [Ekberg 2007](#), and the non-inferiority margin for the primary composite endpoint is 10%.
- For the evaluation of superiority, the event rate in the MPA + sCNI arm is 50%.

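### The SAP's statement that overall Type I error is not inflated leaves out the 0.10-level treatment-by-CNI test that chooses the primary population; at planning rates the one-sided error is about 2.6–2.9%, not 2.5%

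*SAP*

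**What the plan says.** Under the heading on testing of CNI effects, SAP 2.5.2 opens with a selection step: "Based on FAS without imputation, treatment by CNI interaction for the composite endpoint" is assessed in a covariate-adjusted logistic model. The consequence depends on the p-value. "If the interaction is not significant at the level of 0.10, i.e. the effects of treatment are similar for each CNI", the primary analysis pools the CNIs. If the test is significant, "then testing will be performed for the 2 CNIs separately, with the tacrolimus subgroup being considered primary". The SAP is redacted directly after those words, and protocol 9.4.2, which has the same rule, breaks off at the same place.

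Under its next heading the SAP lists three steps: (a) non-inferiority on the primary endpoint, (b) non-inferiority on tBPAR, graft loss or death, (c) superiority on the primary endpoint. It then states: "The above hierarchical fixed hypothesis testing procedure will not inflate overall Type I error rate". From this it concludes that "each hypothesis will be tested at the one-sided 0.025 significance level and no multiplicity adjustment is needed". Protocol 9.4.2 says the same. The decision rule in SAP 2.5.2.1 uses an ordinary interval: non-inferiority is claimed "if the upper limit of the 95% CI is below 10" per cent.

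The tacrolimus route is confirmatory. Protocol 9.7 and SAP Section 3 size the trial for both the overall and the tacrolimus-alone populations.

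**The concern.** A fixed sequence controls Type I error when the population it runs on is fixed too. Here the population is picked from the trial's own Month 12 primary-endpoint data. The tacrolimus estimate is positively correlated with the interaction contrast. A chance favourable result in tacrolimus can therefore trigger the switch to tacrolimus and also help the tacrolimus test to succeed. No visible passage counts this step or lowers the level for it.

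At stake is the stated error rate of the primary non-inferiority and superiority claims, above all for a reader of a tacrolimus-primary result.

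**Working it through.** **Inputs.** 1020 per arm; 80% tacrolimus and 20% cyclosporine (816 and 204 per arm); 50% event rate; margin 10 points; one-sided 0.025 (protocol 9.7, SAP Section 3). Cyclosporine is capped at 20% (protocol 3.1). The interaction level is 0.10, taken as two-sided (SAP 2.5.2).

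**Reproducing the plan's power.** The unpooled normal formula for non-inferiority is Φ(0.10/√(0.5/n) − 1.96). It gives 99.5%, 98.1% and 95.1% for n = 1020, 816 and 653, which matches Table 9-1 (>99, 98, 95) and the statement that "the study has at least 95% power to demonstrate non-inferiority". Superiority at −7 points, with a continuity correction, gives 87.9% and 79.6% for n = 1020 and 816; Table 9-1 prints 87 and 79.

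**Type I error of the whole visible procedure, both strata at the null.**
- Z_T and Z_C are the standardised tacrolimus and cyclosporine results.
- Pooled: Z_P = √0.8·Z_T + √0.2·Z_C.
- Interaction: Z_I = √0.2·Z_T − √0.8·Z_C.
- corr(Z_P, Z_I) = √0.16 − √0.16 = 0, so the pooled branch keeps 2.5%.
- corr(Z_T, Z_I) = √0.2 = 0.447.
- Error = 0.025 × 0.90 + P(Z_T < −1.96 and |Z_I| > 1.645) = 0.0225 + 0.0064 = **0.0289**.

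Without the correlation the second term would be 0.025 × 0.10 = 0.0025. Given a switch (10% of trials when there is no true heterogeneity), the false-claim rate is 0.0064/0.10 = 6.4%.

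With fewer cyclosporine patients the total is 2.79% at 85/15 and 2.69% at 90/10.

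**The planned test is adjusted and uses observed data only.** This weakens the correlation by a factor that the documents do not give. Assumed factors:

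| Factor | Tacrolimus-branch part | Total |
|---|---|---|
| 1.0 (unadjusted) | 0.64% | 2.89% |
| 0.9 | 0.57% | 2.8% |
| 0.7 | 0.44% | 2.7% |
| 0.5 | 0.35% | 2.6% |

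Simulated adjusted logistic fits, with treatment by six regions, assumed Month 1 to Month 12 eGFR correlations of 0–0.9 and 0–10% missing data, gave 2.62–2.84%.

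**Binomial simulation, unadjusted interaction test, non-inferiority null (+10 points in both strata).**

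| Control rate, tacrolimus / cyclosporine | Error at 0.025 | Error at 0.0215 |
|---|---|---|
| 50 / 50 | 2.89% | about 2.5% |
| 50 / 60 | 2.99% | about 2.5% |
| 50 / 70 | 3.03% | 2.63% |

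With unequal control rates, equal risk differences are not equal odds ratios. The logistic interaction is then not zero and the switch is more frequent (14.6% at 50/70). Adjusted tests in such settings gave 2.8–3.1%.

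**Cyclosporine truly worse.** With tacrolimus at the margin and cyclosporine 2, 3, 5 or 10 points worse, the unadjusted test gives 2.41%, 2.28%, 2.20% and 2.39%, all below 2.5%.

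**The case against.** The strongest reply is that the sentence is correct as written: it refers to the hierarchy directly above it, under a separate heading, and that hierarchy does control error. This stands for steps a–c. But the sentence speaks of the overall rate, and the unadjusted 0.025 is drawn from it, so a reader will take it to cover the primary claim, including how its population was chosen.

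Second, the redaction falls where a rule for the separate-CNI branch would stand. A reader might infer that the plan has no such rule. The documents do not support that, and the point is confined to the visible text. The later statement that no multiplicity adjustment is needed is not redacted, however.

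Third, the effect is slight, the selection rule was specified in advance, and tacrolimus-alone inference was a design goal. All true. These facts limit the size of the problem but do not make the error statement cover the selection step.

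Fourth, the adjusted-test range rests on assumed covariate strength, and its lower end (factor 0.5) is assumed rather than simulated. That also stands.

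**Conclusion.** The error statement holds for steps a–c in a population fixed in advance. It does not hold for the visible procedure as a whole. At the planning rates, with both strata at the null, the one-sided error is 2.89% for an unadjusted interaction test and about 2.6–2.8% for an adjusted one, against 2.5%. The excess, roughly 0.1–0.5 points over the scenarios examined, lies wholly in the tacrolimus branch. If the pooled branch was taken, only the wording is at issue.

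Three stronger readings should be avoided.
- 2.9% is not a ceiling: unequal control rates give about 3.0%.
- The error is not always inflated: it can fall below 2.5% when cyclosporine is truly worse.
- A reader might infer that success in either CNI counts, which would give about 4.9%. The visible text names tacrolimus as primary in that branch, so this does not follow.

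**What to change.** **In any case.** Reword the statement in SAP 2.5.2 and protocol 9.4.2: error control refers to steps a–c within the selected population and does not cover the selection step. Report which branch was taken. If it was tacrolimus, show the pooled FAS result beside it. This needs no patients and no new data.

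This is probably the whole remedy. Last patient first treatment was 26 January 2016 (protocol, Amendment 1), this SAP is dated 27 February 2018, and SAP Section 1 confines these tests to Month 12. The Month 12 analysis has probably been run.

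**Only if it has not been run**, choose one of two options.
1. Fix the pooled FAS as primary and make tacrolimus non-inferiority a later fixed step. Its power is 98.1% before allowing for the power of the steps ahead of it. The cost is that the headline result then averages over CNIs.
2. Keep the selection and test both possible primary populations at a reduced one-sided level, with a matching confidence interval. About 0.0215 (a 95.7% interval, since 1 − 2 × 0.0215 = 0.957) restores 2.5% at equal control rates. At 50/70 the error is still about 2.6%, so covering unequal rates needs a slightly lower level.

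Price of 0.0215: superiority power at −7 points, on the basis that reproduces Table 9-1, falls from 87.9% to 86.5% pooled and from 79.6% to 77.7% in tacrolimus. FAS non-inferiority power stays at 99.4% and 97.8%. Tacrolimus per-protocol Month 12 non-inferiority power falls from 95.1% to 94.4%, just under the stated 95%, which would have to be restated.
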